8.1. Statistical methods

8.1.1. Analysis of continuous data

Summary statistics (number of patients, mean, standard deviation, median, maximum, and minimum) will be calculated.

If a test is performed for comparison of before and after administration of Lyrica, a paired t-test will be used. If changes before and after administration of Lyrica (change = value after administration - value before administration) are compared between subgroups, the effect of the factor will be tested (P-value will be calculated) with an analysis of covariance model using the factor to be evaluated as a factor and the value before administration as a covariate, and the least squares mean, standard error, and 95% confidence interval of change will be calculated for each subgroup.

8.1.2. Analysis of categorical data

Frequency (e.g., number of patients) and its proportion (composition ratio) of each category will be calculated.

8.1.3. Analysis of binary data

Frequency and its proportion will be calculated. If the confidence interval of proportion is calculated, a 2-sided 95% confidence interval (exact method) will be calculated.

If the proportion is compared between subgroups, Fisher’s exact test and Cochran-Armitage test (exact method) will be performed for the relationships with nominal scale data and

ordinal scale data, respectively, and the risk ratio and risk difference with their 95% confidence intervals will be calculated.

8.2. Statistical analyses

8.2.1. General description of patients

- **Number of institutions and patients to be surveyed by establishment category**

Number of institutions and patients with their proportion by establishment category are to be calculated for the patients whose survey forms collected:

- National, public and private university hospitals
- National hospitals established by the Ministry of Health, Labour and Welfare
- Prefectural and municipal hospitals
- Public organizations
- Hospitals established by corporations and individuals not described above
- General practitioners and clinics

Additionally, mean, minimum, and maximum of the number of patients per institution will be calculated.

- **Patient disposition**

For registered patients, number of registered patients, patients whose survey form was collected, and patients included in the safety analysis set and efficacy analysis set will be tabulated. Also, number of patients whose survey form was not collected, patients excluded from safety analysis and efficacy analysis and number of patients by reason for exclusion will be tabulated.

- **Listing of discontinuations and dropouts**

Number and proportion of discontinued patients will be tabulated by timing of discontinuation (≤ 4 weeks, >4 to ≤ 13 weeks, >13 to ≤ 26 weeks, >26 to ≤ 52 weeks, >52 to ≤ 78 weeks, >78 to ≤ 104 weeks, and >104 weeks) in the safety analysis set. In addition, the number and proportion of patients will be tabulated by reason for discontinuation.

- **Listing of excluded patients**

Listings of patients excluded from safety analysis and efficacy analysis, and reasons for exclusion will be prepared.

8.2.2. Patient demographics and treatment history

- **Patient demographics**

The following patient demographics will be tabulated in the safety analysis set and efficacy analysis set in accordance with Section 8.1.

- Sex [male, female]
- Age at the start of treatment (continuous data)
- Age category at the start of treatment [<15 years, ≥15 to <65 years, ≥65 years]
- Age category at the start of treatment [<65 years, ≥65 to <70 years, ≥70 to <75 years, ≥75 to <80 years, ≥80 to <85 years, ≥85 years]
- Inpatient/outpatient status at the initial prescription [inpatient, outpatient]
- Height at the start of treatment (by sex) (continuous data)
- Body weight at the start of treatment (by sex) (continuous data)
- Body weight category at the start of treatment (by sex) [<40 kg, ≥40 to <50 kg, ≥50 to <60 kg, ≥60 kg]
- Name of target disease (i.e., diagnosis of neuropathic pain) [by disease name]
- Duration of target disease (i.e., diagnosis of neuropathic pain) (continuous data)
- Severity of target disease (i.e., diagnosis of neuropathic pain) [mild, moderate, severe]
- Pain score (continuous data)
- Name of underlying disease (i.e., primary disease of nerve damage that cause neuropathic pain) [by disease name]
- Hepatic impairment [no, yes (mild, moderate, severe)]
- Renal impairment [no, yes (mild, moderate, severe)]
- Hemodialysis [no, yes]
- Creatinine clearance category [<15 mL/min, ≥15 to <30 mL/min, ≥30 to <60 mL/min, ≥60 mL/min]
- Hyperalgesia [no, yes]
- Past medical history [no, yes]
- Complications [no, yes]

The following number and proportion of patients will be tabulated by SOC and PT in the safety analysis set.

- Breakdown of underlying disease
- Breakdown of past medical history
- Breakdown of complications

The following number and proportion of patients will be tabulated in the safety analysis set and efficacy analysis set.

- Presence or absence and breakdown of concomitant medications
- Presence or absence and breakdown of concomitant non-medication therapies
- Presence or absence and breakdown of prior medications

- **Information on administration of Lyrica**

The following information on administration of Lyrica will be tabulated in the safety analysis set.

- Duration of administration [≤ 4 weeks, >4 to ≤ 13 weeks, >13 to ≤ 26 weeks, >26 to ≤ 52 weeks, >52 to ≤ 78 weeks, >78 to ≤ 104 weeks, >104 weeks]
- Timing of administration (at the start of treatment) [morning, noon, evening, bedtime, other]
- Timing of drug administration (at the start of treatment) [before meal, after meal, other]
- Daily dose (continuous data)
- Daily dose (at the start of treatment) [≤ 25 mg, >25 to ≤ 75 mg, >75 to ≤ 150 mg, >150 to ≤ 300 mg, >300 to ≤ 600 mg, >600 mg]
- Daily dose (maximum) [≤ 25 mg, >25 to ≤ 75 mg, >75 to ≤ 150 mg, >150 to ≤ 300 mg, >300 to ≤ 600 mg, >600 mg]
- Daily dose (final) [≤ 25 mg, >25 to ≤ 75 mg, >75 to ≤ 150 mg, >150 to ≤ 300 mg, >300 to ≤ 600 mg, >600 mg]

Dosing period is from the day of initial dose in the survey to the day of last dose, including period of dose interruption. Daily dose (continuous data) will be calculated as the mean dose during the entire period in which Lyrica was actually administered to each patient excluding pro re nata (PRN) prescription, and the mean, standard deviation, and mode will be calculated in the safety analysis set.

8.2.3. Safety analysis

8.2.3.1. Adverse reactions

- **All adverse reactions**

Number and proportion of patients with adverse reactions will be tabulated by SOC and PT.

- **Serious adverse reactions**

Number and proportion of patients with serious adverse reactions will be tabulated by SOC and PT.

- **Details of adverse reactions**

Number and proportion of patients with adverse reactions will be tabulated by SOC and PT for each of the following items.

- Seriousness [Serious, non-serious]
- Expected/unexpected [expected, unexpected]
- Number of days to onset [≤ 4 weeks, >4 to ≤ 13 weeks, >13 to ≤ 26 weeks, >26 to ≤ 52 weeks, >52 to ≤ 78 weeks, >78 to ≤ 104 weeks, >104 weeks]
- Action taken [discontinuation, dose interruption or reduction, dose increase]

- Outcome [not recovered, recovered with sequelae, recovering, resolved/recovered, unknown]

If the same adverse reaction (the same PT) occurs more than once in the same patient, tabulation of the number of patients experiencing the adverse reactions will be handled as follows.

- Seriousness: Serious if both serious and non-serious reactions occurred
- Expected/unexpected: Unexpected if both expected and unexpected reactions occurred
- Number of days to onset: Number of days to onset of the first reaction
- Action taken: If more than one action were taken, select one action in the following order of priority: discontinuation, dose interruption or reduction, dose increase, none
- Outcome: Outcome of the reaction lastly occurred in the patient

- **Major investigation items**

Number and proportion of patients will be calculated for the following major investigation items.

- Peripheral edema and edema-related events*^a
*: Adverse events of the cardiovascular and respiratory systems will also be checked.
- Dizziness, somnolence, loss of consciousness, syncope, and potential for accidental injury
- Vision-related events

Furthermore, number and proportion of patients with major investigation items will be tabulated for each SOC and PT by seriousness, action taken, and outcome.

For “peripheral edema and edema-related events”, number and proportion of patients with events will be tabulated by presence or absence of weight increase. Two types of definitions of patients with weight increase are used: 1) those with “weight increased (MedDRA PT)” reported as an adverse reaction; 2) those with body weight increased by 7% or more from baseline at least once. Number and proportion of patients with adverse reactions will be tabulated for each SOC and PT by presence or absence of peripheral edema. In addition, number and proportion of patients with the following adverse reactions will be tabulated by presence or absence of peripheral edema to evaluate the relationship between peripheral edema and cardiovascular and respiratory events.

^a: Occurrence of cardiovascular and respiratory events will be examined in patients with peripheral edema and edema-related events.

- Events coded to the MedDRA PT “arrhythmia”, “atrial fibrillation”, “cardiovascular disorder”, “cardiac failure congestive”, “hypertension”, “hypotension”, “palpitations”, “tachycardia”, or “dyspnoea”
 - Events coded to the MedDRA SOC “Cardiac disorders”, “Vascular disorders”, or “Respiratory, thoracic and mediastinal disorders”
- **Pancreas-related events, thyroidal function-related events, change in appetite and activity-related events, suicide-related events, withdrawal symptom and rebound phenomenon-related events, and skin disorder-related events**

Number and proportion of patients will be calculated for each event.

- **Patients with special background**

Number and proportion of patients with adverse reactions and serious adverse reactions will be calculated by SOC and PT in the following subgroups and other patients.

- Elderly patients
- Pediatric patients
- Patients with renal impairment
- Patients with hepatic impairment

Patients with renal impairment are defined as those with “Renal impairment: yes” or creatinine clearance of less than 60 mL/min.

- **Relationship between dosage and administration and development of adverse reactions**

In order to evaluate the relationship between dosage and administration and development of adverse reactions, number and proportion of patients with adverse reactions will be tabulated by SOC and PT for patients whose creatinine clearance and the initial daily dosage are ≥ 60 mL/min and 150 mg, respectively, and patients whose creatinine clearance and the initial daily dosage are ≥ 30 to < 60 mL/min and 75 mg, respectively.

- **Relationship between prior and concomitant medications and development of adverse reactions**

In order to evaluate the relationship between the drug class of prior or concomitant medications and adverse reactions, number of patients with adverse reactions will be tabulated for each PT by target disease (i.e., diagnosis of neuropathic pain) and drug class of prior or concomitant medications. However, concomitant medications used after the initial onset of the event will be excluded from tabulation. For target disease, diseases with number of patients analyzed of approx. 100 or more will be examined.

- **Occurrence of adverse reactions by inclusion in/exclusion from the safety analysis set**

A listing of adverse reactions in patients excluded from the safety analysis set will be prepared. Moreover, number of patients with adverse reactions will be tabulated by SOC and PT.

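### When a reaction recurs, only the last episode's outcome is tabulated, so earlier sequelae or non-recovery can drop out of the outcome tables

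*SAP*

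**What the plan says.** Section 8.2.3.1 of the SAP, under the details of adverse reactions, tabulates patients by SOC and PT for several items. It then sets one rule per item for a patient who has the same PT more than once:

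- Seriousness: "Seriousness: Serious if both serious and non-serious reactions occurred".
- Expectedness: "Expected/unexpected: Unexpected if both expected and unexpected reactions occurred".
- Days to onset: "Number of days to onset: Number of days to onset of the first reaction".
- Action taken, if there was more than one: "select one action in the following order of priority: discontinuation, dose interruption or reduction, dose increase, none".
- Outcome: "Outcome: Outcome of the reaction lastly occurred in the patient".

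The outcome categories are "Outcome [not recovered, recovered with sequelae, recovering, resolved/recovered, unknown", so sequelae and non-recovery are kept apart from full recovery. The list is not stated to be a ranking.

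For the major investigation items the same section says that "number and proportion of patients with major investigation items will be tabulated for each SOC and PT by seriousness, action taken, and outcome". It gives no other rule for repeated episodes there. Section 7 adds that a missing outcome is tabulated as unknown.

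**The concern.** Three of the five rules keep the graver category when episodes differ. Outcome can also be ordered by gravity, yet its rule looks only at which episode came last. A patient whose first episode left sequelae and whose second episode of the same PT resolved is counted once, as resolved/recovered. The sequelae appear nowhere in that table.

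The survey's purpose is long-term safety. Section 5 pools data from the preceding 13-week investigation with this survey, so episodes over up to 104 weeks can fall into one patient-by-PT cell. Outcome is one of only three breakdowns specified for the major investigation items, and the final analysis supports the reexamination application. A table that can drop sequelae or non-recovery makes reactions look more reversible than the collected data show.

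**Working it through.** The SAP attaches no figure to this rule, so there is none to reproduce. Its only design figure, 310 patients, is context: 1 − (1 − 0.0097)^310 = 0.951, which meets the stated 95% but does not bear on this point.

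**Check by enumeration.** Take two episodes of one PT, each with one of the 5 outcome categories: 5 × 5 = 25 ordered pairs. Compare the last-episode rule with a graver-category rule. The SAP ranks no outcomes, so the order is an assumption: *recovered with sequelae*, *not recovered*, *recovering*, *unknown*, *resolved/recovered*, gravest first. The rules differ when the first episode ranks above the last:

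| First episode | Lower-ranked last outcomes that replace it | Pairs |
|---|---|---|
| recovered with sequelae | not recovered, recovering, unknown, resolved/recovered | 4 |
| not recovered | recovering, unknown, resolved/recovered | 3 |
| recovering | unknown, resolved/recovered | 2 |
| unknown | resolved/recovered | 1 |
| resolved/recovered | none | 0 |

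Total: 4 + 3 + 2 + 1 = 10 of 25 pairs.

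- An earlier grave outcome (the first two rows) is replaced in 4 + 3 = 7 pairs. Swapping the top two ranks leaves this count unchanged.
- In those 7 pairs the patient is shown as resolved/recovered in 2, unknown in 2, recovering in 2 and not recovered in 1. For sequelae alone, 1 of the 4 replacements is resolved/recovered.
- The two unknown pairs include a last episode whose outcome is merely missing, because section 7 tabulates it as unknown. A known sequela can thus be overwritten by a blank.

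These are counts of possible pairs, not of patients.

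**Does the last outcome give current status?** The rule selects the reaction that occurred last. That reaction's resolution says nothing about sequelae left by an earlier one, and it does not close an earlier episode still recorded as not recovered. The table therefore shows neither the worst outcome nor a reliable latest status.

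**Scale.** The number affected in a PT row is at most the patients with that PT who had a repeat, and in practice only those whose earlier outcome was graver. The SAP gives neither share. For illustration only, assume that 5% to 20% of patients with a reaction have a repeat. A reaction with 1% incidence is expected in 310 × 0.01 = 3.1 patients, so 3.1 × 0.05 = 0.16 to 3.1 × 0.20 = 0.62 would have a repeat. That is a ceiling: for a rare PT the usual effect is nil, but a single case would be a visible part of the row.

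**The case against.** The strongest reply is that this is a clear, programmable convention and not a contradiction. Onset takes the first reaction and outcome the last, a coherent start-and-end pairing; days to onset is not a worst-case rule either, so outcome is not the only departure from one. Testing in the survey is exploratory, and section 9 plans listings of adverse reactions, of serious adverse reactions and of the major investigation items, where single episodes may still be visible.

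Most of this stands. The rule is unambiguous, and nothing outside the outcome tables is touched. Two parts do not carry the defence. Onset has no order of gravity, while outcome does. The listings' columns are not specified, and a listing does not correct a summary table.

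A reader might infer more: that the tables will show patients as serious, discontinued and fully recovered, a combination that no episode had. The SAP does not support this. It names the items as breakdowns and nowhere specifies a cross-table of seriousness, action and outcome. Also, if the first episode led to discontinuation, section 2.1 leaves only 7 days of follow-up and the first visit after that, and Appendix 1 drops safety data collected after the safety evaluation date. A recurrence in that window is possible but unlikely to be common. Nor can it be said that earlier sequelae are generally reported as recovered; that needs the last episode to have resolved.

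**Conclusion.** The point holds as a minor weakness in a summary rule. For recurrent PTs, the outcome tables lose an earlier *recovered with sequelae* or *not recovered* whenever the last episode's outcome is better or unknown. Measured against a graver-category rule, the loss runs in one direction by construction.

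The conclusion rests on two readings: that the repeat rules also govern the major investigation items, for which no other rule is given, and that sequelae and non-recovery are the two gravest of the listed outcomes. The number of patients affected cannot be estimated from the SAP. Incidence, serious-reaction counts, subgroup tests and efficacy results are unaffected.

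**What to change.** Either of two changes to section 8.2.3.1 is enough.

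1. Give outcome a stated priority order, as is already done for action taken: for example *recovered with sequelae*, *not recovered*, *recovering*, *unknown*, *resolved/recovered*. Keep the last-episode outcome as a second column, since a graver-category rule alone would show non-recovery for a patient whose later episode resolved. The place of *unknown* must be fixed explicitly. If it ranked below *resolved/recovered*, as the order of the SAP's category list might suggest, a patient whose last episode has an unknown outcome would move to resolved/recovered because an earlier one resolved.
2. Keep the last-episode rule and add, per PT, the number of patients with any episode *recovered with sequelae* or *not recovered*.

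Say in the same place that the rule applies to the major investigation items. The cost is a line or two of text, a sort order or a count in the program, one extra column, and slightly less favourable outcome tables. No new data are needed, and no sample size or test changes.

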6.1. Safety endpoints

- Adverse reactions: Adverse events determined to be related to Lyrica by the investigator or the sponsor
- Adverse events: All-causality adverse events
- Serious adverse reactions or adverse events: Adverse reactions or adverse events determined to be serious by the investigator or the sponsor
- Major investigation items:

- Peripheral edema and edema-related events*
*: Adverse events of the cardiovascular and respiratory systems will also be checked.
- Dizziness, somnolence, loss of consciousness, syncope, and potential for accidental injury
- Vision-related events

Events to be handled as major investigation items are defined as events of safety specification in the European risk management plan of Lyrica (important identified risk: peripheral edema and edema-related events; dizziness, somnolence, loss of consciousness, syncope, and potential for accidental injury; vision-related events).

- Accident-related events:

Accident-related events are defined as events coded to the MedDRA SMQ “accidents and injuries”. These events will be evaluated for adverse events.

- Pancreas-related events:

Pancreas-related events are defined as events coded to the MedDRA SMQ “acute pancreatitis (narrow scope)”, those coded to the MedDRA HLG “exocrine pancreas conditions” or the MedDRA HLT “pancreatic neoplasms malignant (excl islet cell and carcinoid)”, and those related to the laboratory test results of primary pancreatic parameters of serum amylase, lipase, and trypsin among those coded to the MedDRA SOC “Investigations”.

- Thyroidal function-related events:

Thyroidal function-related events are defined as events coded to the MedDRA SMQ “thyroid dysfunction”.

- Change in appetite and activity-related events

Change in appetite and activity-related events are defined as events coded to the MedDRA PT “decreased activity”, “decreased appetite”, “increased appetite”, or “hypokinesia”.

- Euphoric mood-related events:

Euphoric mood-related events are defined as events coded to the MedDRA PT “euphoric mood”.

- Suicide-related events:

Suicide-related events are defined as events coded to the MedDRA SMQ “suicide/self-injury”. These events will also be evaluated for adverse events.

- Withdrawal symptom and rebound phenomenon-related events:

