8.2.3.2. Adverse events

- **All adverse events**

Number and proportion of patients with adverse events will be tabulated by SOC and PT.

- **Adverse events by serious/non-serious**

Number and proportion of patients with serious adverse events will be tabulated by SOC and PT. Non-serious adverse events will be tabulated in the same manner.

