8.2.3.3. Other endpoints

- **Body weight**

Summary statistics specified in Section 8.1.1 will be calculated by time point as defined in Appendix 1 for measurements and their changes from baseline.

Number and proportion of patients with the following adverse reactions will be tabulated for patients whose body weight increased by 7% or more from baseline at least once and other patients.

- Abnormal glucose tolerance-related events: Events coded to the MedDRA HLGT “glucose metabolism disorders (incl diabetes mellitus)” or the MedDRA HLT “carbohydrate tolerance analyses (incl diabetes)”
- Dyslipidemia-related events: Events coded to the MedDRA HLGT “lipid metabolism disorders” or “lipid analyses”
- Events coded to the MedDRA PT “arrhythmia”, “atrial fibrillation”, “cardiovascular disorder”, “cardiac failure congestive”, “hypertension”, “hypotension”, “palpitations”, “tachycardia”, or “dyspnoea”
- Events coded to the MedDRA SOC “Cardiac disorders”, “Vascular disorders”, or “Respiratory, thoracic and mediastinal disorders”

- **Laboratory parameters**

Summary statistics specified in Section 8.1.1 will be calculated by time point as defined in Appendix 1 for laboratory parameters and their changes from baseline.

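### The edema-split cardiovascular and respiratory tables count adverse reactions only, although the SAP promises a check of adverse events, and the accident-related group has no patient count in section 8

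*SAP*

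**What the plan says.** Section 6.1 separates two terms. One is "Adverse reactions: Adverse events determined to be related to Lyrica by the investigator or the sponsor"; the other is "Adverse events: All-causality adverse events".

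Peripheral edema and related events are a major investigation item. Sections 2.2, 6.1 and 8.2.3.1 all attach the same note to it: "Adverse events of the cardiovascular and respiratory systems will also be checked". Footnote a in section 8.2.3.1 adds: "Occurrence of cardiovascular and respiratory events will be examined in patients with peripheral edema and edema-related events".

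The table rule in section 8.2.3.1 is "In addition, number and proportion of patients with the following adverse reactions will be tabulated by presence or absence of peripheral edema", with the stated aim "to evaluate the relationship between peripheral edema and cardiovascular and respiratory events". It covers two groups, one of nine named PTs and one of three SOCs. The preceding sentence plans a general SOC/PT table by edema status, also for adverse reactions.

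Section 8.2.3.2 covers the all-causality side: "Number and proportion of patients with adverse events will be tabulated by SOC and PT". Serious and non-serious adverse events are tabulated in the same way. None of these tables is split by edema.

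Section 6.1 also defines accident-related events through the MedDRA SMQ on accidents and injuries and says they are to be assessed on an adverse-event basis. Section 8 does not mention this group.

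**The concern.** The edema tables are meant to show whether cardiovascular and respiratory problems go together with edema. If only adverse reactions enter, the outcome has already passed through a judgement on whether the drug caused it. An event coded as congestive cardiac failure that both investigator and sponsor called unrelated would be missing from the comparison in which it matters most. The result would then depend partly on how causality was attributed in patients with and without edema.

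For accidents, an endpoint group with a stated analysis basis has no analysis that delivers it. A reader would see PT rows but not how many patients had any accident-related event.

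**Working it through.** The SAP gives no numerical figure on this point to reproduce. The check sets the passages side by side and counts.

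**Step 1: what is promised under the edema item.** The note in sections 2.2, 6.1 and 8.2.3.1 uses the defined term, adverse events, which section 6.1 makes all-causality. Footnote a says where the examination takes place: in patients with edema. Read together, they call for all-causality cardiovascular and respiratory events to be looked at by edema status.

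**Step 2: what is specified.**

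| Table | Basis | Split by edema |
|---|---|---|
| 8.2.3.1, group of nine PTs | adverse reactions | yes |
| 8.2.3.1, group of three SOCs | adverse reactions | yes |
| 8.2.3.1, general SOC/PT table | adverse reactions | yes |
| 8.2.3.2, all / serious / non-serious | adverse events | no |

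Of the two cardiovascular/respiratory groups split by edema, 2 are on adverse reactions and 0 on adverse events. No specified table relates edema to all-causality cardiovascular or respiratory events. Nor does section 8.2.3.1 say whether edema status is itself taken from adverse reactions or from all adverse events.

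**Step 3: what the filter does.** Hold edema status fixed. Let p1 and p0 be the proportions of patients with and without edema who have at least one event of the group, whatever the cause. Let a1 and a0 be the shares of those patients with at least one such event judged related. The planned tables show p1 × a1 and p0 × a0, so their ratio is

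(p1 × a1) / (p0 × a0) = (p1 / p0) × (a1 / a0).

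This equals the all-causality ratio only if a1 = a0. If events are more readily attributed to the drug in patients with edema, the ratio is pushed up; in the opposite case it is pushed down. The SAP gives neither share, so size and direction cannot be derived.

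**Step 4: accident-related events.** Beyond the major investigation items, section 6.1 lists eight event groups: accident, pancreas, thyroid, appetite/activity, euphoric mood, suicide, withdrawal/rebound and skin. Section 8.2.3.1 gives a patient count for six: pancreas, thyroid, appetite/activity, suicide, withdrawal/rebound and skin. That leaves 8 − 6 = 2, accident and euphoric mood. Euphoric mood is a single PT, so its PT row already is its patient count. The accident group is an SMQ, and a patient with events under two of its PTs appears in two rows, so the rows do not add up to patients. One group is left with no patient count.

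**The case against.** The strongest reply is that the SAP chose adverse reactions on purpose. The tables stand under the heading for adverse reactions and name that basis. The bare word events proves little, because the SAP uses it generically inside reaction tables: the rows of these very tables begin with it. The promise to check adverse events could be met by the SOC/PT tables in section 8.2.3.2 and the listings in section 9. Further analyses are allowed under section 8.2.3.5.

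Part of this stands. A reader might infer a contradiction from the word events in the purpose sentence ("to evaluate the relationship between peripheral edema and cardiovascular and respiratory events") alone; that wording is too loose to carry it. The conflict rests on the note with the defined term, read with footnote a. The unsplit tables and listings meet a general check, but they do not give the comparison by edema status. Additional analyses under section 8.2.3.5 are optional and reported selectively, so they do not replace a specified table.

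Other stronger readings also go too far:

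- **Weight tables.** Section 8.2.3.3 uses the same two groups on the same basis ("Number and proportion of patients with the following adverse reactions will be tabulated for patients whose body weight increased by 7% or more"), but states no purpose concerning adverse events. These tables do not add to the conflict.
- **Accidental injury.** One might say that the major investigation item covers accidents, or that it is reported only pooled with the dizziness and consciousness terms. Neither is right. Section 6.1 defines that item by the European risk management plan, not the SMQ, and section 8.2.3.1 also tabulates the major items by SOC and PT. How far the two definitions overlap cannot be checked from the SAP.
- **Suicide-related events.** One might infer that the adverse-event analysis was left out. Section 6.1 says these events are assessed for adverse events as well, and the count in section 8.2.3.1 does not name its basis. This is a wording ambiguity, not an omission.

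**Conclusion.** The point holds in two parts. First, both cardiovascular/respiratory groups split by edema are counted on adverse reactions only, while the note on the edema item and footnote a point to all-causality events in patients with edema. Second, the accident-related SMQ group has a stated adverse-event basis in section 6.1 and no patient count in section 8.

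The first part assumes that the note uses adverse events in the sense defined in section 6.1. Only events judged unrelated by both investigator and sponsor are lost, since either one's judgement makes an event a reaction. A reader might infer that the edema association will be understated or overstated; the SAP contains nothing to support either.

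Severity is minor to moderate. Section 4.1 calls the testing exploratory, no decision rule depends on these tables, and no data are lost. What suffers is the completeness of the safety results and their independence from causality attribution.

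**What to change.** - In section 8.2.3.1, add an adverse-event version of the two cardiovascular/respiratory tables by presence or absence of peripheral edema. Keep the adverse-reaction version beside it, and state for each whether edema status is taken from adverse reactions or from all adverse events.
- In section 8.2.3.2, add the number and proportion of patients with at least one adverse event in the accidents and injuries SMQ.
- As a wording clarification only, state whether the suicide-related count is given for adverse reactions, adverse events or both.

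The cost is some SAP wording and a few extra tables from data already coded. The survey is recorded as completed, and no new data collection is needed.
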